#### 2.1.2.10.2.10 Other items specified as exploratory

- (1) Regarding "No longer required ongoing medical care" defined in Category 6 on the 7-point ordinal scale, period to improvement by at least 2-rank on a 7-point ordinal scale will be recalculated in the case that the end of treatment during tapering of steroid therapy according to the patient's condition has been defined. And similar analysis to the primary endpoint will be performed. The analysis will be performed only in the FAS. The end of treatment is defined as "use of dexamethasone 4 mg (equivalent to prednisolone 25 mg or methylprednisolone 20 mg) or less."
- (2) Similar analysis to that in Section 2.1.2.10.2.2 will be performed for the period from baseline to shifting to Category 5 on a 7-point ordinal scale. Patients who are in Category 3 or 4 at baseline on a 7-point ordinal scale will be included in the analysis. Definitions of event/censoring are presented in Table 2.3.
- (3) Similar analysis to that in Section 2.1.2.10.2.2 will be performed for the period from baseline to improvement by at least 1 rank on a 7-point ordinal scale. Definitions of events/censoring are presented in Table 2.3.

### 2.1.2.11 Safety Evaluation

#### 2.1.2.11.1 Adverse Event (AE)

The names of adverse events (AEs) described in the Case Report Form will be read using the specified version of MedDRA. AEs will be tabulated in SOC and PTs unless otherwise specified. When the causality of an AE with the study drug is considered "related", the event is considered as an adverse drug reaction (ADR).

##### 2.1.2.11.1.1 AE and ADR

- (1) Analysis set : SP
- (2) Analysis item : AE and ADR
- (3) Time point : start of treatment to Day 28
- (4) Analytical method :
  - 1) Regarding AEs, serious AEs (SAEs), AEs leading to death, AEs leading to dose reduction of the study drug, AEs leading to discontinuation of the study, and significant AEs, the number of events, the number of patients who developed such events and the proportion will be calculated by treatment group. ADRs will be calculated in the same way.
  - 2) Regarding AEs and ADRs, the number of events, number of patients who developed such events and the proportion will be summarized by treatment group and by SOC and PT (number of patients, number of events, %). Similarly, the data will be summarized by time period.
  - 3) A list of AEs will be prepared Analysis set : Randomized Patients

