2 Observation and Examination Schedule

Item	Screening	Date of allocation	Observation period ⁵⁾												Discontinuation/ Exit Test ⁶⁾
			Day 0	Day 1	Day 2	Day 3	Day 4	Day 5	Day 6	Day 7	Day 8	Day 9	Day 10	Day 11 ~14	Day 15 ~28
Acceptable window	To Day 0	-2 days ⁷⁾	—	—	—	—	—	+1 day ⁷⁾	—	—	—	—	—	—	+1 day
Informed consent	●														
Medical history/current medical conditions	●														
Subject characteristics	●														
Height and weight	●														
Inclusion and exclusion criteria	●														
Percutaneous oxygen saturation (SpO2)	●														
Allocation		●													
Study drug administration ¹⁾			●	●	●	●	●	●	○	○	○	○	○		
7-point ordinal scale ²⁾			●	●	●	●	●	●	●	●	●	●	●	●	
Oxygen requirement			●	●	●	●	●	●	●	●	●	●	●	●	
Arterial blood gas analysis (PaO2, PaCO2, A-aDO2, others)			● ³⁾					●							●
Inflammatory markers, cytokines			● ³⁾		●		●								●
Chest HRCT or plain chest CT or Chest X-ray			●					●							●
Physical examination			●					●							●
Vital sign			●					●							●
12-lead ECG			●					●							●
Laboratory tests (blood chemistry, hematology and urinalysis)			●					●							●
Pregnancy test (urine or blood sample)			●												
adverse events ⁴⁾				●									●		
Concomitant medication/therapy		●	—									●			

● : Will be performed in all the subjects ○ : Will be performed only in the subjects who continue to receive the study drug after Day 5.

1) Inhalation administration will be started on the morning of Day 1 and performed twice daily (morning, evening) for 5 days, in principle (up to 10 days).

2) Will be evaluated every day during the period between Day 1 and Day 28. Use or no use of a ventilator will be included in this evaluation.

3) Will be performed prior to study drug administration.

4) Only the adverse events that have occurred until Day 14 after the start of study drug administration. may be collected and entered in the electronic case report form. Serious adverse events related to the study drug administration will be collected until Day 28.

- 5) Assessment of efficacy on the 7-point ordinal scale and oxygen requirement will be performed after completion of the second dose (inhalation) of the day.
- 6) Will be performed on the day of discontinuation if study drug administration has been prematurely discontinued before Day 5, or on the day of the last dose in the case that the last day is not Day 5.
- 7) Except 7-point ordinal scale and oxygen requirement.

3 Study Administrative Structure

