5.2.2.1 Incidence of AEs and SAEs

Information on AEs occurring from the start of study drug administration until Day 14 will be collected in this study. For SAEs related to the study drug, those occurring until Day 28 will be collected. The number of subjects with AEs and the incidence of AEs will be calculated by seriousness, system organ class (SOC) and/or preferred term (PT), and severity by treatment group.

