14.1 Definition of AE

An AE is any unfavorable or unintended sign (including abnormal laboratory changes), symptom, or disease occurring in an assigned subject from the start of study drug administration, whether or not related to the study drug. Events occurring before the start of study drug administration will be treated as a current medical condition in this study.

AEs required to be entered in the eCRF will be those occurring from the start of study drug administration to Day 14 in this study. SAEs related to the study drug should be collected until Day 28.

Moreover, the subject's current medical condition is not considered an AE unless the severity worsens or the incidence increases after study drug administration. If the investigators judge that the change in a laboratory test value is an unfavorable event for the subject, the event will be assessed as an AE.

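### The SAP's AE tables run to Day 28, but after Day 14 the protocol collects only drug-related SAEs, so incidences labelled to Day 28 can only be correct or too low

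*SAP*

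**What the plan says.** SAP 2.1.2.11.1.1 gives a single window: "start of treatment to Day 28". It governs a list that opens "Regarding AEs, serious AEs (SAEs), AEs leading to death, AEs leading to dose reduction of the study drug" and goes on to AEs leading to study discontinuation and significant AEs, with ADRs handled in the same way. The denominator is the Safety Population. The section also asks for a summary by time period but defines no periods. The severity tables in SAP 2.1.2.11.1.2 state no window of their own.

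The protocol gives a narrower collection rule, and gives it four times:

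- Section 14.1: "AEs required to be entered in the eCRF will be those occurring from the start of study drug administration to Day 14", and then "SAEs related to the study drug should be collected until Day 28".
- Section 5.2.2.1, which defines the safety endpoint: "Information on AEs occurring from the start of study drug administration until Day 14 will be collected in this study", and "For SAEs related to the study drug, those occurring until Day 28 will be collected".
- Section 2, schedule footnote 4: AEs up to Day 14, after which "Serious adverse events related to the study drug administration will be collected until Day 28".
- Section 14.10.1: SAEs of any causality are reported to the sponsor up to Day 14, and only related ones from then to Day 28.

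SAP section 3 declares no change to the planned analysis, so the longer window is not presented as a deliberate departure. For concomitant and standard drugs and therapies (SAP 2.1.2.5 to 2.1.2.8) the SAP does stop at Day 14.

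**The concern.** A table labelled to Day 28 invites the reader to take its proportions as 28-day incidences. Under the protocol's rule they are not. For Days 1 to 14 the numerator holds all events. For Days 15 to 28 it holds only serious events that the investigator judged related.

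The incidence of AEs and SAEs is the trial's only safety endpoint (Protocol 5.2.2), and Protocol section 25 foresees use of the results in regulatory submissions. Protocol 4.4 names progression of respiratory failure, ARDS and multiple organ failure as part of the natural course of the disease. If such an event starts after Day 14 and is judged unrelated, it is not collected. If it is fatal, it is missing from the count of AEs leading to death, while the same patient appears as Category 1 on the ordinal scale, which is rated daily to Day 28. Two tables in one report could then disagree on deaths.

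**Working it through.** The plan states no figure on this point, so there is nothing to reproduce. The check sets the two windows side by side and works out the direction and unit size of the error.

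| Event class | Collected, onset to Day 14 | Collected, onset Days 15-28 | SAP table window |
|---|---|---|---|
| AEs, any causality | all | related SAEs only | to Day 28 |
| SAEs | all | related only | to Day 28 |
| AEs leading to death | all | related only | to Day 28 |
| ADRs | all | serious ones only | to Day 28 |
| Significant AEs (non-serious by Protocol 14.5) | all | none | to Day 28 |

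**Direction, SAEs.** Let N be the patients in the group, S the patients with an SAE by Day 14, and L the further patients whose first SAE starts on Days 15-28. Of these, r of the S and q of the L have a related SAE, with q ≤ L.

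- Tabulated incidence = (S + q)/N; true 28-day incidence = (S + L)/N. Since q ≤ L, the table is correct or too low.
- Related share that a reader would derive = (r + q)/(S + q); true share = (r + q)/(S + L). The numerators are equal and the first denominator is no larger, so the share is correct or too high. The same argument holds for fatal AEs.

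**Unit size.** Protocol section 18 plans 40 active and 20 control patients. One patient whose only event is uncollected changes incidence by 1/40 = 2.5 points or 1/20 = 5.0 points.

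**Illustration for SAEs (assumed counts).** N = 60, S = 8, r = 2.

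- L = 4, q = 0: 8/60 = 13.3% against 12/60 = 20.0%; share 2/8 = 25.0% against 2/12 = 16.7%.
- L = 4, q = 1: 9/60 = 15.0% against 12/60 = 20.0%; share 3/9 = 33.3% against 3/12 = 25.0%.
- L = 6, q = 1: 9/60 = 15.0% against 14/60 = 23.3%; share 3/9 = 33.3% against 3/14 = 21.4%.

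**All AEs (assumed counts).** Here the share has no fixed direction, because late non-serious ADRs are also uncollected. Take 60 AEs by Day 14, 12 of them related, and 20 later AEs, of which one is a collected related SAE. The derived share is 13/61 = 21.3%. The true share is 14/80 = 17.5% if 2 of the 20 are related, 16/80 = 20.0% if 4 are, and 20/80 = 25.0% if 8 are.

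**The case against.** Several points on the other side are sound.

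- **Deaths are not lost.** A reader might infer that any unrelated death on Days 15-28 disappears. The documents do not support that. Collection is limited by when the event occurs, and Protocol 14.8 has AEs followed to resolution as far as possible, with the outcome recorded. An unrelated AE that starts by Day 14 and proves fatal later is therefore in the data. Only unrelated fatal events with onset after Day 14 are missing from the AE table. All-cause deaths are already visible through the daily category summary to Day 28 (SAP 2.1.2.10.2.8, in the FAS) and the listing in SAP 2.1.2.11.1.3.
- **The related share is not a planned statistic.** The SAP tabulates AEs and ADRs separately and specifies no ratio. A reader might infer that the share is inflated throughout. That is certain in direction only for SAEs and fatal AEs.
- **The rule is the same in both blinded arms**, and dosing ends by Day 10 (Protocol 10.3), so all-cause collection covers treatment plus at least four days. The main harm is to absolute incidences, not to the comparison between groups.
- **Day 28 is needed as an outer limit** for the related SAEs that are collected until then, and a summary by period is planned.

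What this does not remove is the mismatch itself. The periods are undefined, a listing gives no incidence, and nothing in the SAP tells the reader that the collection rule narrows after Day 14. A footnote would correct the label but leave one proportion built on two rules.

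**Conclusion.** The point stands as a mismatch between analysis window and collection window. Followed as written, SAP 2.1.2.11.1.1 yields incidences labelled to Day 28 for AEs, SAEs, ADRs and fatal AEs that are correct only if no uncollected event starts on Days 15-28, and otherwise too low. The unit effect is 2.5 points (active) or 5.0 points (control) per patient whose only event is uncollected, at the planned 40 and 20. The total effect cannot be stated, because the documents give no event rates.

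A by-period summary spanning Day 14 would compare all events with related SAEs only. A reader might take the resulting fall as wholly artificial. Part of it may be real, since dosing has ended by then, so the documents support only that it is at least partly an artefact. Likewise, every SAE collected on Days 15-28 is an ADR by construction, but that does not describe the Day 28 table as a whole, which also holds every SAE from Days 1-14.

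The conclusion assumes that sites follow the protocol's collection rule and that occurrence means onset. The SAP should be corrected. The efficacy analyses are not affected.

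**What to change.** In SAP 2.1.2.11.1.1, and in the severity tables of 2.1.2.11.1.2:

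1. Set the window for the AE, SAE, fatal-AE, significant-AE and ADR incidence tables to events with onset from start of treatment to Day 14.
2. Define the periods of the by-period summary, with Day 14 as a cut point.
3. Report drug-related SAEs with onset on Days 15-28 in a separate table whose title states that only related SAEs were collected in that period.
4. For all-cause deaths to Day 28, refer to the existing Category 1 summary (SAP 2.1.2.10.2.8) and the death listing (2.1.2.11.1.3).

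The cost is SAP wording and table labels, with no new data. The one trade-off is that late related SAEs appear outside the main SAE table.

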10.3 Administration of study drug

Administration of study drug will start in the morning of Day 1 (twice daily, in the morning and evening between Day 1 and Day 5).

In the active treatment group, 250 µg/vial of sargramostim will be dissolved in 4 mL of physiological saline, and 2 mL of which will be administered twice daily (in the morning and evening) using an inhaler for 5 days, in principle (up to 10 days). In the control group, 2 mL of physiological saline will be administered twice daily (in the morning and evening) using an inhaler for 5 days, in principle (up to 10 days).

Approximately 10-15 minutes will be taken for one inhalation administration which shall be continue until the prepared solution has been depleted. During the inhalation administration, air cleaner or similar will be available for prevention against infection for healthcare workers and other patients.

The start date and time of the study drug administration should be recorded in the eCRF. Details of the preparation and dispensing of the study drug should be in accordance with the procedures specified separately.

All subjects may continue to receive inhalation administration of the study drug at the discretion of the investigators for up to Day 10 from Day 6 onward. After Day 6, the dosage and administration should be the same as that in the first 5 days.

Occurrence of serious allergic or anaphylactic reactions after administration of sargramostim has been reported. If a serious allergic or anaphylactic reaction occurs, administration should be discontinued and appropriate therapy should be initiated. The investigators shall follow up at least 1 hour after inhalation administration to ensure that no clinical symptoms such as acute hypersensitivity reactions (e.g., facial or extremity swelling, cough, urticaria, decreased consciousness, respiratory distress) are observed.

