14.5 Significant AEs

A significant AE is not an SAE, but is judged to be of special interest due to its clinical significance. A non-SAE leading to study drug discontinuation will be regarded as a significant AE.

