14.8 Observation of AEs

The investigators shall observe the occurrence of AEs carefully through medical interview, medical examination, etc. from the start of study drug administration. If any AE is observed, appropriate measures should be taken, and the AE shall be followed up by the investigators until the AE disappears

or resolves as far as possible. However, if the investigators judge that further follow-up observation is not necessary and discontinue follow-up observation, or if the subject refuses it, the reason shall be entered in the eCRF.

For any AEs that have occurred, information of the name of the event, date and time of onset (or date and time when the event was found), severity, seriousness (serious/non-serious), action taken with the study drug (if yes, its contents), treatment for the event (yes or no), outcome, date and time of outcome (when the event disappeared, the date and time of disappearance), and causality to the study drug should be entered in detail in the eCRF.

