15.1 Study drug discontinuation

If the subject meets any of the following criteria at any time before the second dose on Day 5, study drug administration for the subject shall be discontinued.

- (1) The subject has started to use invasive ventilator or ECMO.
- (2) The WBC count of the subject exceeds 25,000/ μ L.
- (3) An AE has occurred and the investigators judged it difficult to continue study drug administration.
- (4) The subject was found to be pregnant or suspected to be pregnant, or the subject wished to be pregnant or breastfeeding.
- (5) The subject was discharged from the hospital (including transfer to another hospital) and cannot continue to receive the study drug.

[Rationale]

- (1) It was set because accurate specified dose of the study drug is thought difficult.
- (2) and (3) It was set in order to ensure the safety of the subject.
- (4) It was set because the safety of sargramostim administration during pregnancy or lactation has not been established.
- (5) The possibility of discontinuation due to inevitable accident was considered.

Discontinuation of study drug administration does not necessarily preclude discontinuation of participation of the subject in the clinical study, and a policy was decided to follow-up and to collect the data on Japanese COVID-19 patients who participated in the clinical study whenever possible.

If an event meets the criteria for study drug discontinuation, the investigators shall follow the following procedures.

- The investigators shall immediately discontinue the study drug administration for the subject and perform observations/examinations at the time of discontinuation within 1 day of the discontinuation of study drug administration.
- If the event does not meet the criteria of “15.2 Withdrawal of subject from the study” and the observations/examinations can be performed, the subject will continue to participate in the study and continue the scheduled study procedures other than the administration of the study drug.
- The date and reason for discontinuation of study drug administration, as well as comments on discontinuation as appropriate, will be entered in the eCRF.

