15.2 Withdrawal of a subject from the study

A subject who meets any of the following criteria shall be withdrawn from study participation.

- (1) The subject was found not to meet the inclusion criteria or to meet the exclusion criteria and to be ineligible for the clinical study according to the results of medical examinations, etc. performed after start of the clinical study.
- (2) The subject or the legally acceptable representative has requested to terminate the clinical study or to withdraw his/her consent.
- (3) The subject was dead.
- (4) The investigators judged that continuation of the clinical study is not desirable for the subject due to other reasons.

[Rationale]

- (1) It was set as a general item to ensure safety of the subject and to properly evaluate the study.
- (2) It was set in accordance with the principles of the Declaration of Helsinki and the GCP.
- (3) Since continuous observation cannot be performed, it was set as a discontinuation criterion due to inevitable accident.
- (4) In addition to above mentioned criteria, it was set as a general item for discontinuation criteria so that the investigators can judge appropriateness to continue the clinical study.

If an event occurs to meet the criteria for withdrawal of subjects from the study, the investigators shall follow the following procedures.

- The date of discontinuation (the date on which discontinuation was judged and the date of last dose, if possible) and the reason for discontinuation, as well as comments on discontinuation if necessary, will be entered in the eCRF.

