##### 2.1.2.11.1.4 Significant AEs

A significant AE includes a non-serious AE leading to discontinuation of the study drug and regarded as a non-SAE that is considered to be of special interest due to its clinical significance. A list of significant AEs will be prepared.

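### The SAP's adverse-event summary has no category for events that stop study drug, so non-fatal serious events that stop dosing in patients who stay in follow-up are not counted by arm as such

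*SAP*

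**What the plan says.** SAP 2.1.2.11.1.1 1) sets out the top-level AE table. For each arm it gives events, patients and proportions for all AEs, SAEs, AEs leading to death, and "AEs leading to dose reduction of the study drug, AEs leading to discontinuation of the study, and significant AEs". ADRs are to be calculated in the same way.

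The protocol describes what can happen to dosing and to participation:

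- **Stopping drug for an AE.** Protocol 15.1 (3) gives as a ground: "An AE has occurred and the investigators judged it difficult to continue study drug administration". It does not distinguish serious from non-serious events. Section 10.3 also calls for dosing to stop after a serious allergic or anaphylactic reaction.
- **Dose level.** Section 10.3 describes one dosage for all dosing days: "After Day 6, the dosage and administration should be the same as that in the first 5 days".
- **What follows a drug stop.** Under 15.1, provided no withdrawal criterion is met and assessments are possible, "the subject will continue to participate in the study and continue the scheduled study procedures other than the administration of the study drug".
- **Leaving the study.** Section 15.2 lists ineligibility, withdrawal of consent, death and a general clause: "The investigators judged that continuation of the clinical study is not desirable for the subject due to other reasons". An AE is not named.
- **Significant AEs.** Protocol 14.5: "A non-SAE leading to study drug discontinuation will be regarded as a significant AE". SAP 2.1.2.11.1.4 agrees: "A significant AE includes a non-serious AE leading to discontinuation of the study drug".

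**The concern.** The categories in the AE table do not match the actions the protocol provides for. The one dose action it gives for an AE is to stop the drug, and that is the action with no row. Dose reduction has a row but no step in the protocol behind it. Discontinuation of the study has a row, but a patient who stops drug is normally kept in the study.

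The result is an asymmetry. Non-serious AEs that stop dosing are counted by arm, because they are significant AEs by definition. Serious AEs that stop dosing have no corresponding count. At stake is how readily a reader of the safety tables can see, by arm, how often events ended dosing in a fixed-dose trial.

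**Working it through.** The SAP states no figure to reproduce. The check follows each kind of AE that stops dosing through the categories of SAP 2.1.2.11.1.1 1), using the definitions in protocol 14.5, 15.1 and 15.2.

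| AE that stops dosing | Row, apart from the overall AE and SAE rows |
|---|---|
| (a) Non-serious | Significant AEs |
| (b) Serious, fatal | AEs leading to death |
| (c) Serious, non-fatal, and it also ends study participation | AEs leading to discontinuation of the study |
| (d) Serious, non-fatal, patient stays in follow-up | None |

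Only type (d) is missed, and it is the course that 15.1 describes for a patient who stops drug and meets no withdrawal criterion. A non-fatal serious allergic reaction handled as in 10.3, with the patient then followed up, is an example from the protocol itself.

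**Where type (d) does appear.**
- As an event: the SAE row of the same table (and its ADR counterpart if related), the SOC/PT and severity tables, the AE list, the list of deaths and SAEs (SAP 2.1.2.11.1.3), and the per-subject SAE narratives with causality (protocol 17.2.3).
- As a patient: the by-arm table of reasons for discontinuation in SAP 2.1.2.9. That table gives no AE term, seriousness or causality.

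Protocol 15.1 also lists invasive ventilation/ECMO (1) and a high white cell count (2) as grounds separate from an AE (3). If the recorded reasons follow that list, which is an assumption because the eCRF coding is not given, an AE behind ground (1) or (2) would not show as an AE-related stop in 2.1.2.9.

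**Scale.** Protocol section 18 plans 60 subjects at 2:1:
- active arm 60 × 2/3 = 40; control arm 60 × 1/3 = 20
- one patient of type (d): 1/40 = 2.5% of the active arm, or 1/20 = 5% of the control arm
- two active-arm patients of type (d), with no other events: 2/40 = 5% in the SAE row, and 0 under leading to death, dose reduction, discontinuation of the study, and significant AEs

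The documents give no expected number of such events, so these are illustrations and not predictions.

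**Are the data there?** Protocol 14.8 has the action taken with study drug entered for every AE. Dosing ends by Day 10 and all AEs are collected to Day 14 (14.1), so any AE that stops dosing falls inside the collection window.

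**The case against.** The strongest case against is that this is a matter of table labels.

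- **Every SAE is already counted by arm, listed and narrated, and SAP 2.1.2.9 counts drug stops by reason.** This stands, and it limits the point. In 60 patients a reader could link the narratives to the list of drug stops. That is still reconstruction from listings, not a planned count by arm.
- **The SAP breaks no protocol commitment.** This also stands. The safety endpoint is the incidence of AEs and SAEs, and protocol 17.2.3 asks for no table of events leading to discontinuation.
- **Discontinuation of the study may be a slip for the study drug.** Possible: protocol section 11 runs the two ideas together. But the same SAP sentence refers to the study drug when it means the drug, and protocol 15.1 and 15.2 keep the two outcomes apart. If it is a slip, the wording still needs correcting.
- **The new row could mix worsening COVID-19 with intolerance.** True of any all-cause AE row in this population. The matching ADR row helps, because it applies the causality assessment.

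A reader might go further and infer three things that the documents do not support. First, that every serious AE that stops dosing escapes these rows: types (b) and (c) above do not. Second, that serious events go unreported or that tolerability would be misstated: the SAE row would show them. Third, that the protocol forbids dose reduction: it fixes the dosage and provides no reduction step, but contains no express prohibition.

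**Conclusion.** The point holds in a narrow form. SAP 2.1.2.11.1.1 1) lacks a category for AEs and ADRs leading to discontinuation of study drug, and the neighbouring categories do not fill the gap for non-fatal SAEs in patients who remain in follow-up. What is missing is the by-arm link between the serious event and the drug stop; the event itself is reported.

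The effect is confined to safety reporting, and no efficacy result changes. The conclusion rests on reading study and study drug as different terms, as protocol 15.1 and 15.2 do, and on the protocol being followed on dosage and follow-up. It is a minor gap, worth closing because the correction is specific and nearly free.

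**What to change.** In SAP 2.1.2.11.1.1 1):

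1. Add a row, by arm, for AEs leading to discontinuation of the study drug (serious and non-serious), with the same row for ADRs. It may take the place of the dose-reduction row or stand beside it.
2. Derive it from the action-taken item recorded for each AE under protocol 14.8.
3. Keep AEs leading to discontinuation of the study as a separate row.
4. Reconcile the SAP's terms for stopping drug, leaving the study and significant AEs with protocol 14.5, 15.1 and 15.2.

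The cost is a line or two of SAP wording and one table row each for AEs and ADRs. No new data are needed. The change concerns reporting only and leaves the protocol's dosing and stopping rules as they are.
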